3.1 Inclusion Criteria

Informed Consent and Willingness to Participate

1. Documented willingness and ability to sign an informed consent of the participant and/or Legally Authorized Representative

Age Criteria and Performance Status

2. Age 18 or older
3. ECOG performance status of 0 or 1.

Nature of Illness and Disease Status Criteria

4. Patients must have a histologically confirmed diagnosis of mature peripheral T-cell or NK-cell lymphoma according to the WHO classification, with hematopathology review at the participating institution. Eligible histologies are:

- Peripheral T-cell lymphoma, not otherwise specified
- Anaplastic large cell lymphoma, ALK-negative
- Anaplastic large cell lymphoma, ALK-positive
- Angioimmunoblastic T-cell lymphoma
- Nodal peripheral T-cell lymphoma with TFH phenotype
- Follicular T-cell lymphoma
- Indolent T-cell lymphoproliferative disorder of the GI tract
- Extranodal NK-/T-cell lymphoma
- Enteropathy-associated T cell lymphoma
- Monomorphic epitheliotropic intestinal T-cell lymphoma
- Hepatosplenic T-cell lymphoma
- Subcutaneous panniculitis-like T-cell lymphoma
- Transformed mycosis fungoides

5. Patients must have failed at least one prior regimen, including:

- Recurrence of disease after a documented complete response (CR)
- Progression of disease after a partial response (PR) to the prior regimen
- Partial response, stable disease (SD) or progressive disease (PD) at the completion of the prior treatment regimen. If a patient has PR to prior regimen without PD, there must be biopsy-proven* residual disease that is measurable (see #6 below)

* Exception can be granted by the PI if a biopsy is not feasible and/or safe.

6. Patient must have measurable disease by CT or PET scan, with one or more sites of disease $\geq 1.5\text{cm}$ in longest dimension.

7. Be willing to provide tissue from a fresh core or excisional biopsy (performed as standard of care) of a tumor lesion prior to starting study therapy or from archival tissue of a biopsy that was performed after the most recent systemic therapy. Exception can be granted by the PI if a biopsy is not feasible and/or safe.

Participant MRN (COH Only):	Participant Initials (F, M, L):
Institution:	

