11.0 ENDPOINT EVALUATION CRITERIA/MEASUREMENT OF EFFECT

11.1 Response/Progression

Disease response/progression will be evaluated using 2014 Lugano Classification (see [Appendix B](#))^{8,11}. Participants who meet the definition of progressive disease per Lugano Classification should be evaluated using the LYRIC criteria¹⁰ (see [Appendix C](#)). The ORR and CR rate will also be estimated according to the International Harmonization Project response criteria (Cheson 2007).⁹

PET-CT or diagnostic quality CT of the neck, chest, abdomen, and pelvis (N/C/A/P) with IV contrast will be performed at baseline (within the screening window, 28 days) prior to initiation of study therapy, and then after initiation of study therapy during cycle 4 and every 4 cycles thereafter until disease progression or off study therapy. Refer to [study calendar \(footnote r\)](#) for disease staging at EOT. Disease staging will be by either PET/CT (preferred) or CT scan, but, in patients with FDG-avid disease, it will be preferred (but not mandatory) to have PET/CT at baseline, Cycle 4 and at least every 8 cycles thereafter. In patients with FDG-avid disease, CR must be confirmed with PET/CT. Patients who enter CR with study therapy can be monitored with diagnostic quality CT scans thereafter until disease progression. MRI may be performed at the investigator's discretion for lesions not well-visualized by CT, or if CT with intravenous contrast is contraindicated. PET-CT and CT results will be read by radiology at each study site and investigator response based on radiology reading will be performed. Lymphoma response assessment based on PET-CT/CT will be based on the 2014 Lugano Classification ([Appendix B](#)).^{8,11}

Note: if there is no evidence of neck involvement by lymphoma at baseline, CT of chest, abdomen and pelvis (C/A/P) can be performed instead of N/C/A/P at subsequent re-staging.

Following initial screening, and unless clinically indicated, bone marrow specimens will be collected only to confirm CR.

For patients with progression of disease on imaging, it is strongly recommended that a confirmatory biopsy (performed as standard of care) be obtained whenever possible. Note that only an FDG-negative PET scan will be considered complete remission in patients whose tumor was FDG-avid at baseline.

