APPENDIX B: 2014 LUGANO RESPONSE CRITERIA

Response	Site	CT-Based Response	PET-CT Based Response
Complete Response	Lymph nodes and extralymphatic sites	Complete radiologic response (all of the following) 
 Target nodes/nodal masses must regress to ≤ 1.5 cm in longest diameter (LD_i). No extralymphatic sites of disease. 	Complete metabolic response (even with a persistent mass) 
 Score $\leq 3^*$ with or without a residual mass on 5-point scale[†]. It is recognized that in Waldeyer's ring or extranodal sites with high physiologic uptake or with activation within spleen or marrow (e.g., with chemotherapy or myeloid colony-stimulating factors), uptake may be greater than normal mediastinum and/or liver. In this circumstance, complete metabolic response may be inferred if uptake at sites of initial involvement is no greater than surrounding normal tissue even if the tissue has high physiologic uptake.
	Nonmeasured lesion	Absent	Not applicable
	Organ enlargement	Rgress to normal	Not applicable
	New lesions	None	None
	Bone marrow	Normal by morphology; if indeterminate, IHC negative	No evidence of FDG-avid disease in marrow
Partial Response		Partial remission (all of the following) 
 Lymph nodes and extralymphatic sites 
 $\geq 50\%$ decrease in SPD of up to 6 target measurable nodes and extranodal sites When a lesion is too small to measure on CT, assign 5 mm X 5 mm as the default value When no longer visible, 0 X 0 mm For a node > 5 mm X 5 mm, but smaller than normal, use actual measurement for calculation 	Partial metabolic response 
 Score 4 or 5[†] with reduced uptake compared with baseline and residual mass(es) of any size At interim, these findings suggest responding disease At end of treatment, these findings indicate residual disease

Response	Site	CT-Based Response	PET-CT Based Response
	Nonmeasured lesion	Absent/normal, regressed, but no increase	Not applicable
	Organ enlargement	Spleen must have regressed by > 50% in length beyond normal	Not applicable
	New lesions	None	None

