	Bone marrow	Not applicable	Residual uptake higher than uptake in normal marrow but reduced compared with baseline (diffuse uptake compatible with reactive changes from chemotherapy allowed). If there are persistent focal changes in the marrow in the context of a nodal response, consideration should be given to further evaluation with MRI or biopsy or an interval scan
No response or stable disease	Stable disease		No metabolic response
	Target nodes/nodal masses, extranodal lesions	< 50% decrease from baseline in SPD of up to 6 dominant, measurable nodes and extranodal sites; no criteria for progressive disease are met	Score 4 or 5† with no significant change in FDG uptake from baseline at interim or end of treatment
	Nonmeasured lesion	No increase consistent with progression	Not applicable
	Organ enlargement	No increase consistent with progression	Not applicable
	New lesions	None	None
	Bone marrow	Not applicable	No change from baseline
Progressive disease	Progressive disease requires at least 1 of the following		Progressive metabolic disease
	Individual target nodes/nodal masses	PPD progression:	Score 4 or 5† with an increase in intensity of uptake from baseline and/or
	Extranodal lesions	An individual node/lesion must be abnormal with: Longest diameter (LDi) > 1.5 cm and Increase by ≥ 50% from PPD nadir and	New FDG-avid foci consistent with lymphoma at interim OR end-of-treatment assessment

Response	Site	CT-Based Response	PET-CT Based Response
		An increase in LD _i or shortest diameter (SD _i) from nadir 0.5 cm for lesions \leq 2 cm 1.0 cm for lesions $>$ 2 cm In the setting of splenomegaly, the splenic length must increase by $>$ 50% of the extent of its prior increase beyond baseline (e.g., a 15-cm spleen must increase to $>$ 16 cm). If no prior splenomegaly, must increase by at least 2 cm from baseline New or recurrent splenomegaly	
	Nonmeasured lesion	New or clear progression of preexisting nonmeasured lesions	None

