1, no uptake above background; 2, uptake \leq mediastinum; 3, uptake $>$ mediastinum but \leq liver; 4, uptake moderately $>$ liver; 5, uptake markedly higher than liver and/or new lesions; X, new areas of uptake unlikely to be related to lymphoma.

Abbreviations:

CT, computed tomography; FDG, fluorodeoxyglucose; IHC, immunohistochemistry; LDi, longest transverse diameter of a lesion; MRI, magnetic resonance imaging; PET, positron emission tomography; PPD, cross product of the LDi and perpendicular diameter; SDi, shortest axis perpendicular to the LDi; SPD, sum of the product of the perpendicular diameters for multiple lesions.

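### The entry size limit (at least 1.5 cm, longest dimension) meets the nodal CT-based CR limit (at most 1.5 cm transverse), leaving a narrow gap for nodal-only disease read by CT

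*Combined protocol and SAP*

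**What the plan says.** **Entry.** Section 3.1, inclusion 6, repeated in the synopsis: "Patient must have measurable disease by CT or PET scan, with one or more sites of disease" at or above 1.5 cm in longest dimension. No axis is named, and nodal and extranodal sites share one limit. Inclusion 5 also admits patients left in partial response by their last regimen without progression. Their residual disease must be measurable under inclusion 6 and biopsy-proven, unless the PI grants an exception.

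**CT-based response, Appendix B.**
- Nodal CR: "Target nodes/nodal masses must regress to" 1.5 cm or less in LDi. The abbreviation list defines LDi as the "longest transverse diameter of a lesion".
- Extranodal CR: "No extralymphatic sites of disease". There is no size allowance.
- PR: at least a 50% "decrease in SPD of up to 6 target measurable nodes and extranodal sites".
- Progression row only: "An individual node/lesion must be abnormal with: Longest diameter (LDi) > 1.5 cm".

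**PET.** Section 11.1: "In patients with FDG-avid disease, CR must be confirmed with PET/CT". It adds that, if the tumour was avid at baseline, only a negative PET counts as complete remission. Section 11.1 and study calendar footnote h make baseline PET/CT in avid disease preferred but optional. Footnote 1 of the schema and of Section 5.1 words it as what will be done.

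**Endpoint.** Section 11.2 counts a documented CR or PR at any point on treatment. Section 12.3.3 speaks of confirmed responses without defining confirmation. Section 12.1.2 continues past stage 1 on one response in the first 7 evaluable patients.

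**The concern.** A size-based CR criterion works only if the node starts above the CR size. Nothing in the plan requires that. Inclusion 6 uses a non-strict limit on an unspecified dimension, while CR uses a non-strict limit in the opposite direction on the transverse diameter. A patient can therefore be eligible on a node that is already within CR size.

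The regression wording in Appendix B states no minimum. For a node at or just under the limit, a change of a millimetre, within what repeat reading could produce, could be recorded as regression to 1.5 cm or less. CR counts in the primary ORR and in the secondary CR rate, and the stage 1 decision turns on a single response. Small residual nodes are a foreseeable way into the trial because inclusion 5 allows entry in partial response.

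**Working it through.** **1. Compare the two limits.**

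| | Entry (3.1, item 6) | Nodal CT-based CR (Appendix B) |
|---|---|---|
| Dimension | longest, axis not named | LDi, transverse |
| Limit | at least 1.5 cm | at most 1.5 cm |

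- If both rules mean the same diameter, they share exactly one value, 1.5 cm.
- If the longest dimension may lie in another plane, the overlap is wider. Illustration: a node 1.6 cm craniocaudally with LDi 1.4 cm meets inclusion 6 and is already within CR size.

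**2. Remove the cases that other rules block.**
- Known FDG-avid disease: a negative PET is needed, so size alone cannot give CR.
- Any extranodal site: it must be absent.
- PR by CT: an unchanged node has an SPD change of 0%, against the required fall of at least 50%.
- Abnormal nonmeasured lesions, organ enlargement, new lesions or abnormal marrow: each prevents CT-based CR.

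What is left is nodal-only disease, all target nodes at or below 1.5 cm transverse, all other CR criteria met, and CT assessment because the disease is non-avid or because no baseline PET was done and avidity is unknown. In the last case the PET rule has no baseline finding to act on.

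**3. Reproduce the plan's figures (Section 12.1.2).**
- Standard error at n = 24: √(0.30 × 0.70 / 24) = 9.35%, the same at 70%; √(0.50 × 0.50 / 24) = 10.2%. The plan states 9.4%-10.2%.
- Maximum exact 95% interval width: 41.8%, at 12/24. The plan states 42%.
- P(at least 1 response in 7 at ORR 35%) = 1 − 0.65⁷ = 95.1%. The plan states at least 95%.

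All three match. The point does not dispute the sample size.

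**4. Size of one false CR in a patient who otherwise would not respond.**
- ORR: 1/24 = 4.2 percentage points. Example: 7/24 = 29.2% (exact 95% CI 12.6-51.1) becomes 8/24 = 33.3% (15.6-55.3).
- Stage 1: one false CR among the first 7 passes the rule with certainty. Without it, the pass probability is 1 − 0.90⁷ = 52% at a true ORR of 10%, and 1 − 0.80⁷ = 79% at 20%.

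**5. Range over the unknown frequency.** Let q be the chance that a non-responder is scored a false CR. The documents do not give q; the values below are assumptions. Apparent ORR = p + (1 − p)q. With true p = 20%:

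| q | Apparent ORR | P(pass stage 1) |
|---|---|---|
| 0 | 20.0% | 79.0% |
| 1/24 | 23.3% | 84.4% |
| 2/24 | 26.7% | 88.6% |
| 10% | 28.0% | 90.0% |

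Given how many conditions must hold together in step 2, the upper rows are the more plausible ones.

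**The case against.** A reader might infer that any patient with a small lesion can enter already in CR and be scored a responder with no shrinkage, so that ORR is biased upward. The documents do not support that.

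- In known avid disease the PET rule in Section 11.1 decides CR, whatever the node size. This stands and removes that group.
- Several eligible histologies are extranodal, and extranodal disease has no CR size allowance. This stands.
- A strictly unchanged node has not regressed, so it fails the plain wording of the nodal CR criterion. This stands for no change at all. It does not cover a trivial change, because no minimum is given.
- The axis argument depends on how inclusion 6 is read. Appendix B itself writes longest diameter beside LDi, and only its abbreviation list says transverse. If inclusion 6 means LDi, the overlap is the single value 1.5 cm. That is a fair reading, but inclusion 6 does not state it.
- The 1.5 cm abnormality threshold stands in the progression row. For baseline, Appendix B asks only that dominant lesions be clearly measurable in two diameters. It therefore cannot be cited as an existing baseline rule that inclusion 6 breaks.
- Section 12.3.3 requires confirmed responses, which might screen out a single noisy reading. The term is undefined, and Section 11.2 says only documented, so the protection is uncertain.
- One patient moves ORR by 4.2 points against a standard error of 9.4%-10.2%. That is true of the final estimate. It is less reassuring at stage 1, where one response decides.

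**Conclusion.** The overlap is in the text, and nothing requires a target node to exceed the CR limit at baseline. Its reach is limited to the subgroup left at the end of step 2 of the working. For such a patient a trivial change could be scored as CR, at 4.2 points of ORR each and a certain pass if it falls within stage 1. This rests on two readings: that the regression wording is met by any decrease, and that a single reading suffices. How often such a patient would enrol is not in the documents; it is probably seldom. This is a minor definitional gap and a cheap improvement, not a demonstrated bias in ORR.

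**What to change.** 1. In inclusion 6 and the synopsis, require at least one node with LDi above 1.5 cm, or an extranodal site of at least 1.5 cm in longest dimension. The second part keeps the present limit, so extranodal entry does not become vague.
2. In Section 11, state that, where measurable disease is nodal, CT-based CR requires regression from a baseline LDi above 1.5 cm.
3. Reconcile the baseline-PET wording in footnote 1 of the schema and Section 5.1 with Section 11.1 and calendar footnote h, so that it is clear when avidity may remain unknown.

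The cost is a few lines of text and a few borderline patients who become ineligible. The design figures in Section 12.1.2 do not change. A node just above 1.5 cm will still need only a small decrease to reach CR size; that belongs to any fixed size limit and is not removed. If enrolment is too far advanced to change eligibility, item 2 alone closes the gap.

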3.2 Exclusion Criteria

Nature of Illness and Disease Status Criteria

- 1.** Patients with adult T-cell leukemia/lymphoma

Prior Therapy and Concomitant Therapy

- 2.** Prior allogeneic hematopoietic stem cell transplantation within the last 5 years.
- 3.** Prior autologous hematopoietic stem cell transplant within the last 60 days.
- 4.** Patients who received prior therapy with an anti-PD-1, anti-PD-L1, or anti-PD-L2 agent without having had evidence of objective response.
- 5.** Patients who received prior therapy with pralatrexate without having had evidence of objective response.
- 6.** Investigational agent or anti-cancer monoclonal antibody (mAb) within 21 days prior to Day 1 of therapy or who has not recovered (i.e. ≤ 1 or at baseline) from adverse events due to agents administered more than 21 days earlier.
- 7.** Prior chemotherapy, targeted small molecule therapy, or radiation therapy within 14 days prior to Day 1 of therapy or who has not recovered (i.e. ≤ 1 or at baseline) from adverse events due to a previously administered agent. Note: Subjects with \leq Grade 2 neuropathy are an exception and may qualify for the study.
- 8.** Antineoplastic biologic therapy or major surgery within 21 days of the first dose of trial medication. If subjects received major surgery more than 21 days ago, they must have recovered adequately from the toxicity and/or complications from the intervention prior to starting therapy.
- 9.** Received live vaccine or live-attenuated vaccine within 30 days prior to Day 1 of protocol therapy. Administration of killed vaccines is allowed.
- 10.** Systemic steroid therapy or on any other form of immunosuppressive therapy within 7 days prior to the first dose of trial treatment.

Participant MRN (COH Only):	Participant Initials (F, M, L):
Institution:	

Other Illnesses and Conditions

- 11. Diagnosis of immunodeficiency.
- 12. Has a known additional malignancy that is progressing or requires active treatment. Exceptions include basal cell carcinoma of the skin or squamous cell carcinoma of the skin that has undergone potentially curative therapy or in situ cervical cancer.
- 13. Congestive heart failure Class III/IV according to the New York Heart Association (NYHA) Functional Classification.
- 14. Known severe hypersensitivity reaction to pembrolizumab, pralatrexate, leucovorin or any excipients.
- 15. Active autoimmune disease that has required systemic treatment in the past 2 years (replacement therapies for hormone deficiencies are allowed). Hemolytic anemia associated with the lymphoma does not exclude a patient from the study.
- 16. Known history of HIV (HIV ½ antibodies).
- 17. Known active Hepatitis B (e.g., HBsAg reactive) or Hepatitis C (e.g., HCV RNA [qualitative] is detected).
- 18. History of active TB infection (Bacillus Tuberculosis).
- 19. Active central nervous system (CNS) involvement by lymphoma, including parenchymal and/or lymphomatous meningitis. Subjects with prior CNS involvement by lymphoma must have a baseline MRI and lumbar puncture at screening that demonstrate no active lymphoma in the CNS.
- 20. Has a history of (non-infectious) pneumonitis/interstitial lung disease that required steroids or current pneumonitis/interstitial lung disease.
- 21. Active, uncontrolled infection requiring systemic therapy.
- 22. Female: Pregnant or breastfeeding
- 23. Expecting to conceive or father children within the projected duration of the trial, starting with the pre-screening or screening visit through 120 days after the last dose of trial treatment
- 24. Has known psychiatric or substance abuse disorders that would interfere with cooperation with the requirements of the trial.
- 25. History or current evidence of any condition, therapy, or laboratory abnormality that might confound the results of the trial, interfere with the subject's participation for the full duration of the trial, or is not in the best interest of the subject to participate, in the opinion of the treating investigator.
- 26. Any other condition that would, in the Investigator's judgment, contraindicate the patient's participation in the clinical study due to safety concerns with clinical study procedures.

Participant MRN (COH Only):

Participant Initials (F, M, L):

Institution:

Noncompliance

27. Prospective participants who, in the opinion of the investigator, may not be able to comply with all study procedures (including compliance issues related to feasibility/logistics).

Eligibility Confirmed* by (Choose as applicable):	Print Name	Signature	Date
 Site PI			
 Authorized study MD			
 Study Nurse			
 Study CRA/ CRC			
 Other: _____			

*Eligibility should be confirmed per institutional policies.

4.0 PARTICIPANT ENROLLMENT

NOTE: Sites must meet activation requirements prior to enrolling participants.

4.1 Pre-Enrollment Informed Consent and Screening Procedures

Diagnostic or laboratory studies performed exclusively to determine eligibility will be done only after obtaining written informed consent. Studies or procedures that are performed for clinical indications (not exclusively to determine study eligibility) may be used for baseline values and/or to determine pre-eligibility, even if the studies were done before informed consent was obtained. The informed consent process is to be fully documented (see Section 16.4), and the prospective participant must receive a copy of the signed informed consent document. Screening procedures are listed in Section 10.0.

4.2 Participant Enrollment

Eligible participants will be registered on the study centrally by the Data Coordinating Center (DCC) at City of Hope. DCC staff are **available between the hours of 8:00 a.m. and 5:00 p.m. PST, Monday through Friday (except holidays).**

- E-mail: [contact]

4.2.1 Slot verification and reservation

Issues that would cause treatment delays should be discussed with the Study PI.

A designated study team member should email the DCC to verify current slot availability, and to reserve a slot for a specific prospective subject (provide DCC with subject initials), including a tentative treatment date. Slots can only be held for a limited time, at the discretion of the study PI.

The DCC should be notified of cancellations of prospective participants holding slots as soon as possible.

4.2.2 Registration Process

Allow up to 24 hours for the DCC to review. To register a participant, the following procedure must be followed:

1. The study team should contact the DCC via email to provide notification regarding the pending registration and communicate desired timeline of the registration, especially if it must be completed promptly to meet the registration window.
2. The study team will email a **Complete Registration Packet** to the DCC, which consists of a copy of the following documents:
 - Registration Cover Sheet ([Appendix F](#))
 - Completed Eligibility Checklist (printed from Section 3.0 of the protocol) with required signature(s)
 - Signed informed consent
 - Signed HIPAA authorization form (if separate from informed consent)
 - Signed subject's Bill of Rights (California only)

3. In some cases, the DCC may request additional documentation prior to registration. Please refer to the Work Instruction – Reviewing Packets and Registering Subjects for more information. A copy of this work instruction can be provided by the DCC, upon request.
4. When all documents are received, the DCC will review and work with the study team to resolve any missing elements. Any missing documents may delay registration. A participant failing to meet all requirements will not be registered and the study team will be immediately notified.
5. The DCC will send a Confirmation of Registration Form, including the subject study number and cohort assignment to:
 - The study team: Site Lead Investigator, treating physician/sub-investigator, protocol nurse, CRC and pharmacy (as needed)
 - The COH Study PI and COH study team designees (including but not limited to study monitor(s) and statistician(s)).
6. Upon receipt of the Confirmation of Registration Form, COH study team will register the patient in OnCore. DCC will register non-COH patients in OnCore.

